8.3.5.2. Exposure During Breastfeeding

An exposure during breastfeeding occurs if:

- A female is found to be breastfeeding while being exposed or having been exposed to study intervention (ie, environmental exposure). An example of environmental exposure during breastfeeding is a female family member or healthcare provider who reports that she is breastfeeding after having been exposed to the study intervention by inhalation, or skin contact.

The investigator must report exposure during breastfeeding to Pfizer Safety within 24 hours of the investigator's awareness, irrespective of whether an SAE has occurred. The information must be reported using the CT SAE Report Form. When exposure during breastfeeding occurs in the setting of environmental exposure, the exposure information does not pertain to the participant enrolled in the study, so the information is not recorded on a CRF. However, a copy of the completed CT SAE Report Form is maintained in the investigator site file.

An exposure during breastfeeding report is not created when a Pfizer drug specifically approved for use in breastfeeding women (eg, vitamins) is administered in accord with authorized use. However, if the infant experiences an SAE associated with such a drug, the SAE is reported together with the exposure during breastfeeding.

8.3.5.3. Occupational Exposure

The investigator must report any instance of occupational exposure to Pfizer Safety within 24 hours of the investigator's awareness using the CT SAE Report Form regardless of whether there is an associated SAE. Since the information about the occupational exposure does not pertain to a participant enrolled in the study, the information is not recorded on a CRF; however, a copy of the completed CT SAE Report Form must be maintained in the investigator site file.

8.3.6. Cardiovascular and Death Events

Not applicable.

8.3.7. Disease-Related Events and/or Disease-Related Outcomes Not Qualifying as AEs or SAEs

Not applicable.

8.3.8. Adverse Events of Special Interest

Not applicable.

8.3.8.1. Lack of Efficacy

This section is not applicable because efficacy is not expected in the study population.

8.3.9. Medical Device Deficiencies

Not applicable.

8.3.10. Medication Errors

Medication errors may result from the administration or consumption of the study intervention by the wrong participant, or at the wrong time, or at the wrong dosage strength.

Exposures to the study intervention under study may occur in clinical trial settings, such as medication errors.

Safety Event	Recorded on the CRF	Reported on the CT SAE Report Form to Pfizer Safety Within 24 Hours of Awareness
Medication errors	All (regardless of whether associated with an AE)	Only if associated with an SAE

Medication errors include:

- Medication errors involving participant exposure to the study intervention;
- Potential medication errors or uses outside of what is foreseen in the protocol that do or do not involve the study participant.

Such medication errors occurring to a study participant are to be captured on the medication error page of the CRF, which is a specific version of the AE page.

In the event of a medication dosing error, the sponsor should be notified within 24 hours.

Whether or not the medication error is accompanied by an AE, as determined by the investigator, the medication error is recorded on the medication error page of the CRF and, if applicable, any associated AE(s), serious and nonserious, are recorded on the AE page of the CRF.

Medication errors should be reported to Pfizer Safety within 24 hours on a CT SAE Report Form **only when associated with an SAE**.

8.4. Pharmacokinetics

Blood samples of approximately 3 mL each, to provide approximately 1.0 mL plasma, will be collected for measurement of plasma concentrations of bosutinib as specified in the [SoA](#). Instructions for the collection and handling of biological samples will be provided in the laboratory manual. The actual date and time (24-hour clock time) of each sample will be recorded.

The actual times may change, but the number of samples will remain the same. All efforts will be made to obtain the samples at the exact nominal time relative to dosing. Collection of samples up to and including 10 hours after dose administration that are obtained within 10% of the nominal time relative to dosing (eg, within 6 minutes of a 60-minute sample) will

not be captured as a protocol deviation, as long as the exact time of the collection is noted on the source document and the CRF/DCT. Collection of samples more than 10 hours after dose administration that are obtained \leq 1 hour away from the nominal time relative to dosing will not be captured as a protocol deviation, as long as the exact time of the collection is noted on the source document and the CRF/DCT.

Blood samples collected in this study will be used to evaluate the plasma PK of bosutinib.

CCI

Genetic analyses will not be performed on these plasma samples. Participant confidentiality will be maintained.

Samples collected for measurement of plasma concentrations of bosutinib will be analyzed using a validated analytical method in compliance with applicable SOPs.

The PK samples must be processed and shipped as indicated in the instructions provided to the investigator site to maintain sample integrity. Any deviations from the PK sample handling procedure (eg, sample collection and processing steps, interim storage or shipping conditions), including any actions taken, must be documented and reported to the sponsor. On a case-by-case basis, the sponsor may make a determination as to whether sample integrity has been compromised.

CCI

8.7. Immunogenicity Assessments

Immunogenicity assessments are not included in this study.

8.8. Health Economics

Health economics/medical resource utilization and health economics parameters are not evaluated in this study.

9. STATISTICAL CONSIDERATIONS

Detailed methodology for summary and statistical analyses of the data collected in this study is outlined here and further detailed in a SAP, which will be maintained by the sponsor. The SAP may modify what is outlined in the protocol where appropriate; however, any major modifications of the primary endpoint definitions or their analyses will also be reflected in a protocol amendment.

9.1. Statistical Hypotheses

Not applicable.

9.2. Analysis Sets

For purposes of analysis, the following analysis sets are defined:

Participant Analysis Set	Description
PK Concentration	The PK concentration population is defined as all participants randomized and treated who have at least 1 bosutinib concentration in at least 1 treatment period.
PK Parameter	The PK parameter analysis population is defined as all participants randomized and treated who have at least 1 of the bosutinib PK parameters of primary interest in at least 1 treatment period.
Safety	All participants randomly assigned to study intervention and who take at least 1 dose of study intervention. Participants will be analyzed according to the product they actually received.

9.3. Statistical Analyses

The SAP will be developed and finalized prior to database lock before any analyses are performed and will describe the analyses and procedures for accounting for missing, unused, and spurious data. This section is a summary of the planned statistical analyses of the primary and secondary endpoints

9.3.1. Pharmacokinetics Endpoint(s)

PK parameters for bosutinib following single dose administration will be derived from the concentration time profiles using non-compartmental methods as data permit. The various bosutinib PK parameters to be assessed in this study; their definition, and method of

determination are outlined in Table 5. In all cases, actual PK sampling times will be used in the derivation of PK parameters.

Table 5. Definitions of PK Parameters

Parameter	Definition	Method of Determination
AUC _{last}	Area under the plasma concentration-time profile from time zero to the time of the last quantifiable concentration (C _{last})	Linear-log trapezoidal method
AUC _{inf} ^a	Area under the plasma concentration-time curve from time zero extrapolated to infinite time	AUC _{last} + (C _{last} */k _{el}) where C _{last} * is the predicted plasma concentration at the last quantifiable time point estimated from the log-linear regression analysis and k _{el} is the terminal phase rate constant calculated by a linear regression through at least 3 data points in the terminal phase of the log-linear concentration-time curve.
C _{max}	Maximum plasma concentration	Observed directly from the data
T _{max}	Time for C _{max}	Observed directly from the data as time of first occurrence
t _{1/2} ^a	Terminal elimination half-life	Log _e (2)/k _{el} , only those data points judged to describe the terminal log-linear decline will be used in the regression.
CL/F ^a	Apparent clearance after oral dose	Dose/AUC _{inf} after oral dose
V _z /F ^a	Apparent volume of distribution after oral dose	Dose/(AUC _{inf} *k _{el}) after oral dose

a. As data permits.

Natural logarithm-transformed AUC_{inf}, AUC_{last} and C_{max} will be analyzed using a mixed effect model with sequence, period and treatment as fixed effects and participant within sequence as a random effect. Estimates of the adjusted mean differences (Test-Reference) and corresponding 90% CIs will be obtained from the model. The adjusted mean differences and 90% CIs for the differences will be exponentiated to provide estimates of the ratio of adjusted geometric means (Test/Reference) and 90% CIs for the ratios.

The following 2 comparisons will be performed:

[figure not shown]
- Treatment B (Test) vs Treatment A (Reference)
- Treatment A (Test) vs Treatment C (Reference)

The plasma PK parameters AUC_{inf}, C_{max}, AUC_{last}, T_{max}, CL/F, V_z/F and t_{1/2} of bosutinib will be summarized descriptively by treatment. For AUC_{inf}, AUC_{last} and C_{max}, a listing of the individual participant ratios (Test-Reference) will be provided for the 2 comparisons described above. Individual participant bosutinib PK parameters for AUC_{inf}, AUC_{last} and C_{max} will be plotted by treatment and overlaid with geometric mean. Bosutinib plasma

concentrations will be listed and summarized descriptively by PK sampling time and treatment. Individual participant and median profiles of the concentration-time data will be plotted by treatment. For summary statistics and median plots by sampling time, the nominal PK sampling time will be used; for individual participant plots by time, the actual PK sampling time will be used.

If an individual participant has a known cause for biased estimate of a PK parameter (due for example to an event such as vomiting before all of the drug is absorbed in the body), this will be footnoted in summary tables and will not be included in the calculation of summary statistics or statistical analyses. Participants who vomited at or before 2 times of median T_{max} after drug administration may be excluded from PK analysis.

CCI

9.4. Interim Analyses

No formal interim analysis will be conducted for this study. As this is an open-label study, the sponsor may conduct unblinded reviews of the data during the course of the study for the purpose of safety assessment.

9.5. Sample Size Determination

A sample size of 28 participants will provide 90% confidence intervals for the difference between treatments of ± 0.0786 and of ± 0.1196 on the natural logarithmic scale for AUC_{inf}

and $\log_e C_{\max}$ respectively with 90% coverage probability. The following table presents the width of 90% confidence interval for different estimated effects:

Parameter	Estimated Effect (100*Test/Reference)	90% CI	CI Width
AUC _{inf}	80%	0.7395, 0.8655	0.1260
	90%	0.8319, 0.9736	0.1417
	95%	0.8782, 1.0277	0.1496
	100%	0.9244, 1.0818	0.1574
	105%	0.9706, 1.1359	0.1653
	110%	1.0168, 1.1900	0.1732
	120%	1.1092, 1.2982	0.1889
C _{max}	80%	0.7098, 0.9017	0.1918
	90%	0.7985, 1.0144	0.2158
	95%	0.8429, 1.0707	0.2278
	100%	0.8873, 1.1271	0.2398
	105%	0.9316, 1.1834	0.2518
	110%	0.9760, 1.2398	0.2638
	120%	1.0647, 1.3525	0.2878

These calculations are based on estimates of within-subject standard deviations of 0.1560 and 0.2373 for $\log_e AUC_{\inf}$ and $\log_e C_{\max}$ respectively, as average intra-subject standard deviations obtained from previously completed bosutinib crossover studies with similar formulations and under similar conditions (clinical studies B1871016, B1871024, B1871035, and B1871061).

If there are participants who withdraw or discontinue treatment and are considered to be non-evaluable with respect to the primary PK objective, additional participants can be enrolled at the discretion of the investigator upon consultation with the sponsor.

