Natural logarithm-transformed bosutinib AUC_{inf} , AUC_{last} and C_{max} will be analyzed using a mixed effect model with sequence, period and treatment as fixed effects and participant within sequence as a random effect. Estimates of the adjusted mean differences (Test-Reference) and corresponding 90% CIs will be obtained from the model. The adjusted mean differences and 90% CIs for the differences will be exponentiated to provide estimates of the ratio of adjusted geometric means (Test/Reference) and 90% CIs for the ratios.

The following 2 comparisons will be performed:

- Treatment B (Test) vs Treatment A (Reference)
- Treatment A (Test) vs Treatment C (Reference)

The plasma PK parameters AUC_{inf} , C_{max} , AUC_{last} , T_{max} , CL/F , V_z/F and $t_{1/2}$ of bosutinib will be summarized descriptively by treatment. For AUC_{inf} , AUC_{last} and C_{max} , a listing of the individual participant ratios (Test-Reference) will be provided for the 2 comparisons described above. Individual participant bosutinib PK parameters for AUC_{inf} , AUC_{last} and C_{max} will be plotted by treatment and overlaid with geometric mean. Bosutinib plasma concentrations will be listed and summarized descriptively by PK sampling time and treatment. Individual participant and median profiles of the concentration-time data will be plotted by treatment. For summary statistics and median plots by sampling time, the nominal PK sampling time will be used; for individual participant plots by time, the actual PK sampling time will be used.

AEs, ECG, BP, pulse rate, and safety laboratory data will be reviewed and summarized on an ongoing basis during the study to evaluate the safety of participants. Any clinical laboratory, ECG, BP, and pulse rate abnormalities of potential clinical concern will be described. Safety data will be presented in tabular and/or graphical format and summarized descriptively, where appropriate.

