3. OBJECTIVES AND ENDPOINTS

Objectives	Endpoints
Primary: 
To estimate the bioavailability of a single 100 mg capsule relative to four 25 mg capsules of bosutinib under fed condition in adult healthy participants.To estimate the effect of a high-fat, high-calorie meal on the bioavailability of a single 100 mg capsule of bosutinib relative to fasted condition in adult healthy participants.	Primary: 
Plasma AUC_{inf} and C_{max} for bosutinib. (AUC_{last} will be used as the primary estimate if AUC_{inf} cannot be reliably estimated).
Secondary: 
To evaluate the plasma PK of bosutinib when administered as capsule formulation to healthy participants under fasted and fed conditions.To evaluate the safety and tolerability of bosutinib when administered as capsule formulation to healthy participants under fasted and fed conditions.	Secondary: 
Plasma AUC_{last}, T_{max}, CL/F, V_z/F and t_{1/2} for bosutinib.Safety laboratory tests and AE monitoring.

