4.2. Scientific Rationale for Study Design

The current study aims to determine the oral bioavailability of the age-appropriate 100 mg capsule relative to the 25 mg clinical capsules when orally administered under fed condition in healthy participants and also to characterize the effect of food on the plasma pharmacokinetics of bosutinib following administration of the proposed 100 mg commercial capsule.

The study is being designed as a crossover study to account for any period effects. Between each sequential dosing of bosutinib, a minimum of 14-day washout is proposed to minimize any residual bosutinib concentrations prior to start of the next period, as bosutinib has a plasma elimination $t_{1/2}$ of approximately 34 hours.

Bosutinib is currently labeled to be administered with food for improved tolerability. Therefore, the evaluation of relative bioavailability assessment in Treatments A and B will be conducted under fed condition using a high-fat, high-calorie meal^{2,3}.

Based on findings from animal studies and its mechanism of action, bosutinib can cause fetal harm when administered to a pregnant woman, therefore, females of child-bearing potential will be excluded from the study. In addition, the use of a highly effective method of contraception is required for male participants with female partners of child bearing potential (see [Appendix 4](#)).

Retained Research Samples will be collected and stored for further analyses which may, for example, provide greater understanding of the study intervention.

CCI

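### Protocol 9.5 states precision that fits only B vs A at 80% assurance, while its text gives 90% coverage and the food-effect comparison A vs C has no precision figure

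*Protocol*

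**What the plan says.** Protocol 9.5 opens its justification with "A sample size of 28 participants will provide 90% confidence intervals for the difference between treatments of" ±0.0786 for log AUCinf and ±0.1196 for log Cmax, "respectively with 90% coverage probability". A table of 14 rows (seven effect sizes for each parameter) applies these half-widths. Neither the sentence nor the table names a comparison. The within-subject SDs are 0.1560 and 0.2373, described "as average intra-subject standard deviations obtained from previously completed bosutinib crossover studies with similar formulations and under similar conditions".

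There are two primary objectives. One is the 100 mg capsule relative to four 25 mg capsules, fed. The other is "To estimate the effect of a high-fat, high-calorie meal on the bioavailability of a single 100 mg capsule" (Protocol 3). Protocol 9.3.1 and SAP 8.2 serve them with B vs A and A vs C respectively. In Protocol Table 3 and SAP Table 1, all 28 participants receive A and B. Only Sequences 1 and 2 (7 + 7 = 14 participants) receive C, always in Period 3. Sequences 3 and 4 have no Period 3.

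The analysis is a "mixed effect model with sequence, period and treatment as fixed effects and participant within sequence as a random effect" (Synopsis, repeated in Protocol 9.3.1 and SAP 8.2). Protocol 9.1 and SAP 4.1 and 4.2 set no hypotheses and no decision rules.

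**The concern.** Because the study is for estimation only, the precision statement in 9.5 is its entire sample-size justification. A half-width that depends on the number of paired observations cannot be the same for a comparison made in 28 participants and one that only 14 can inform. A reader who takes the unlabelled figure as covering both primary comparisons would expect more precision for the food effect than the design can give. Separately, the 90% attached to the half-widths needs checking, because a precision statement is only as good as the probability that goes with it.

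**Working it through.** **Inputs.** SDs s = 0.1560 and 0.2373, 90% two-sided intervals and N = 28 (Protocol 9.5); 7 per sequence, with C in Sequences 1 and 2 only (Protocol Table 3). Pairs below are AUCinf / Cmax.

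**Formula.** Half-width = t(0.95, df) × s × √v × √(χ²(p, df)/df). Here v is the variance factor of the contrast and p is the assurance, meaning the probability that the observed half-width does not exceed the value.

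**Step 1. Reproduce 9.5.** Take B vs A as a 2x2 crossover: v = 2/28, df = 26, t = 1.7056.
- No assurance factor: 1.7056 × 0.1560 × 0.2673 = 0.0711; for Cmax 0.1082. No match.
- p = 0.80, factor √(31.795/26) = 1.1058: 0.0786 / 0.1196. Exact match, and all 14 table rows agree to 4 decimals.
- p = 0.90, factor √(35.563/26) = 1.1695: 0.0832 / 0.1265. No match.

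For comparison, a 14-participant contrast with 12 df and p = 0.80 gives 0.1206 / 0.1835. The printed figures therefore belong to B vs A at 80% assurance.

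**Step 2. B vs A under the planned model.** There are 14 × 3 + 14 × 2 = 70 observations. With participants included, the fixed part has rank 31, which leaves 39 residual df; v stays 2/28. Then t = 1.6849, and the factors are 1.0881 (p = 0.80) and 1.1397 (p = 0.90).
- p = 0.80: 0.0764 / 0.1163.
- p = 0.90: 0.0801 / 0.1218.
- Assurance carried by the printed half-widths: about 87%.

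The printed half-widths thus carry 80% or about 87% assurance, depending on the df basis, and 90% on neither.

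**Step 3. A vs C under the planned model.** The Period 3 and Treatment C indicators coincide. The fixed-effects design has rank 7. Adding the B−A contrast leaves it at 7, but adding A−C raises it to 8. A−C is not estimable, so no half-width exists.

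**Step 4. A vs C under estimable alternatives, p = 0.80.** Assumptions: same SDs when fasted, no dropout, and the Period 3 condition shown.

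Variance factors:
- Paired in 14 participants: v = 2/14 = 0.1429.
- Pooled, Period 3 = mean of Periods 1 and 2: half of (A−B) from 28 participants plus ((A+B)/2 − C) from 14, so v = ¼ × 2/28 + 1.5/14 = 0.125.
- Pooled, Period 3 = Period 1 (or Period 2): add half the Period 1–2 difference, ¼ × 2/28 = 0.0179, so v = 0.1429.

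| Basis | v | df | A vs C half-width | B vs A, same basis | Ratio |
|---|---|---|---|---|---|
| Stand-alone, as in 9.5 (paired, sequence-adjusted) | 0.1429 | 12 | 0.1206 / 0.1835 | 0.0786 / 0.1196 | 1.53 |
| Pooled, Period 3 = mean of Periods 1 and 2 | 0.125 | 39 | 0.1011 / 0.1538 | 0.0764 / 0.1163 | 1.32 |
| Pooled, Period 3 = Period 1 or Period 2 | 0.1429 | 39 | 0.1081 / 0.1644 | 0.0764 / 0.1163 | 1.41 |

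The probability that the A vs C half-width is no larger than the printed one is about 12%, 9% and 3% in these rows.

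**Step 5. On the ratio scale.** At an estimated ratio of 100% on the 12-df basis, A vs C gives exp(±0.1206) = 0.886 to 1.128 for AUCinf (table: 0.9244 to 1.0818) and exp(±0.1835) = 0.832 to 1.201 for Cmax (table: 0.8873 to 1.1271).

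**The case against.** The best defence is that this is a labelling gap with little consequence. The study tests nothing and has no decision rule, the 14-participant basis for C can be read from the design table, and the printed table is arithmetically sound for B vs A. All of that stands, and it limits the severity. It does not supply the missing figure for a primary objective, and it does not rescue the 90%.

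A second objection is that every A vs C width depends on an analysis the plan does not contain. This also stands. A reader might infer that the food-effect interval will simply be some fixed multiple of the printed one. The documents do not support that: as planned there is no A vs C interval, and the multiple depends on the model, the Period 3 assumption and the df basis. A 39-df A vs C width should not be divided by a 26-df B vs A width. Only the direction is stable, since every estimable analysis tried gives a wider interval.

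Third, the coverage wording might just restate the confidence level. The documents do not settle this. On that reading nothing printed is false, but the 80% behind the numbers is not disclosed.

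Finally, a Period 3 restriction sits uneasily with Protocol 4.2: "The study is being designed as a crossover study to account for any period effects". It cannot be tested in this design, so any A vs C figure has to carry it as a stated assumption.

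**Conclusion.** The point holds in a limited form. The half-widths in 9.5 describe B vs A as a stand-alone crossover at 80% assurance. As an assurance level, the written 90% is not delivered on either df basis. The second primary comparison has no precision figure. With the protocol SDs also holding when fasted, no dropout and a stated Period 3 assumption, its half-width at 80% assurance would be 1.53 times that of B vs A on the stand-alone basis, or 1.32 to 1.41 times on the pooled 39-df basis. The fasted SD is an assumption, since 9.5 does not give SDs by feeding condition. On the 12-df basis the SD would have to be 1 − 1/1.53 = 35% lower for A vs C to reach the printed precision.

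A reader might also infer that the sample size is too small. The documents do not support that, because they set no target width for A vs C. The correction should be made, but it changes no decision rule. The non-estimability of A vs C is a separate and more serious matter for the analysis sections.

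**What to change.** In Protocol 9.5 only:
- (a) Label the half-widths and the table as Treatment B vs Treatment A, n=28.
- (b) Replace the coverage wording with 80% assurance (2x2 crossover, 26 df), which changes no number. Alternatively, keep 90% as the assurance, name the df basis, and restate the figures and table: ±0.0832 and ±0.1265 at 26 df (100% rows 0.9202 to 1.0867 and 0.8812 to 1.1349), or ±0.0801 and ±0.1218 at 39 df. The documents do not show which was intended.
- (c) Add an A vs C half-width for the 14 participants who receive C, at the same assurance and on the same type of df basis. For example, 0.121 for AUCinf and 0.184 for Cmax at 80%, 12 df, stating that this assumes no Period 3 effect and the same within-subject SD when fasted.

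The choice of an estimable A vs C model, and its wording in the Synopsis, Protocol 9.3.1, SAP 8.2 and SAP Appendix 1, belongs with the separate estimability point. That change is the one to which the Section 9 clause that "any major modifications of the primary endpoint definitions or their analyses will also be reflected in a protocol amendment" is relevant; relabelling 9.5 alters no endpoint or analysis. The cost is a few lines of text in 9.5 and a less favourable stated precision for the food effect, with no extra participants. The added figure discloses the Period 3 assumption but does not remove the confounding.

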4. STUDY DESIGN

4.1. Overall Design

This will be a Phase 1, randomized, open-label, 3-period, 4-sequence, crossover, single-dose study in approximately 28 healthy participants (7 participants per sequence). Participants will be randomized to 1 of the 4 sequences of treatment described in Table 3.

Table 3. Study design and treatment

Treatment Sequence	Period 1	Washout	Period 2	Washout	Period 3
1 (n=7)	A	At least 14 days between successive bosutinib doses	B	At least 14 days between successive bosutinib doses	C
2 (n=7)	B		A		C
3 (n=7)	A		B		N/A
4 (n=7)	B		A		N/A

Table 3. Study design and treatment

Treatment Sequence	Period 1	Washout	Period 2	Washout	Period 3
--------------------	----------	---------	----------	---------	----------

Treatment A: 1 × 100 mg capsule under fed condition.

Treatment B: 4 × 25 mg capsules under fed condition.

Treatment C: 1 × 100 mg capsule under fasted condition.

Note: “Enrolled” means a participant’s agreement to participate in a clinical study following completion of the informed consent process and screening. A participant will be considered enrolled if the informed consent is not withdrawn prior to participating in any study activity after screening. Potential participants who are screened for the purpose of determining eligibility for the study, but do not participate in the study, are not considered enrolled, unless otherwise specified by the protocol.

Since the mean plasma elimination $t_{1/2}$ of bosutinib is approximately 34 hours (range 18 to 55 hours), there will be a minimum 14-day washout period between each successive bosutinib doses.

Blood samples for bosutinib PK analysis will be collected at the timepoints specified in the [SoA](#).

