8.2. Statistical Analyses

Natural logarithm-transformed AUC_{inf} , AUC_{last} and C_{max} will be analyzed using a mixed effect model with sequence, period and treatment as fixed effects and participant within sequence as a random effect. Estimates of the adjusted mean differences (Test-Reference) and corresponding 90% CIs will be obtained from the model. The adjusted mean differences and 90% CIs for the differences will be exponentiated to provide estimates of the ratio of adjusted geometric means (Test/Reference) and 90% CIs for the ratios.

The following 2 comparisons will be performed:

- *Treatment B (Test) vs Treatment A (Reference).*
- *Treatment A (Test) vs Treatment C (Reference).*

Residuals from the model will be examined for normality and the presence of outliers via visual inspection of plots of residuals vs predicted values and normal probability plots of residuals but these will not be included in the clinical study report. If there are major deviations from normality or outliers, then the effect of these on the conclusions will be investigated through alternative transformations and/or analyses excluding outliers. Justification for any alternative to the planned analysis will be given in the report of the study.

Table 3. PK Parameters to be Summarized Descriptively by Treatment

Parameter	Summary Statistics
AUC_{inf}^* , AUC_{last} , C_{max}	N, arithmetic mean, median, cv%, standard deviation, minimum, maximum, geometric mean and geometric cv%.
T_{max}	N, median, minimum, maximum.
$t_{1/2}^*$	N, arithmetic mean, median, cv%, standard deviation, minimum, maximum.
CL/F^*	N, arithmetic mean, median, cv%, standard deviation, minimum, maximum, geometric mean and geometric cv%.
Vz/F^*	N, arithmetic mean, median, cv%, standard deviation, minimum, maximum, geometric mean and geometric cv%.

*: if data permit.

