10. APPENDICES

Appendix 1. SAS CODE FOR ANALYSES

An example of the PROC MIXED code is provided below:

```
proc mixed data=tab.pk;
  class seq period trt subject;
  model l&var=seq period trt/ ddfm=KR;
  random subject(seq) /subject=subject(seq);
  lsmeans trt;
  estimate 'B vs A' trt -1 1 0 /cl alpha=0.1;
  estimate 'A vs C' trt 1 0 -1 /cl alpha=0.1;
  ods 'Estimates' out=est&var;
  ods 'lsmeans' out=ls&var;
  ods 'covparms' out=cov&var;
  ods 'tests3' out=tst&var;
run;
```

/* Letter assignments for treatments (trt) within the estimate statement above are as follows;

A = Treatment A: 1 × 100 mg capsule under fed condition;
B = Treatment B: 4 × 25 mg capsules under fed condition;
C = Treatment C: 1 × 100 mg capsule under fasted condition;
*/;

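### Protocol 9.5 attaches a 90% probability to half-widths of ±0.0786 and ±0.1196 that are 80% values as calculated, and about 86.5% values under the planned model

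*Protocol*

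**What the plan says.** The sample size argument in Protocol 9.5 is one of precision, not power. It opens with "A sample size of 28 participants will provide 90% confidence intervals for the difference between" treatments, gives the half-widths as ± "0.0786 and of ± 0.1196 on the natural logarithmic scale" for AUCinf and Cmax, and closes the sentence "respectively with 90% coverage probability". A 14-row table then shows the interval and its width at ratios from 80% to 120%. The inputs are "estimates of within-subject standard deviations of 0.1560 and 0.2373" for log AUCinf and log Cmax, averaged over four earlier bosutinib crossover studies. No formula and no degrees of freedom are given, and no comparison is named.

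The design in Protocol 4.1 is a "3-period, 4-sequence, crossover, single-dose study in approximately 28 healthy participants (7 participants per sequence"). All 28 participants are to receive A and B; 14 of them also receive C, in Period 3. SAP 8.2 plans a "mixed effect model with sequence, period and treatment as fixed effects and participant within sequence as a random effect", and SAP Appendix 1 codes it as "model l&var=seq period trt/ ddfm=KR" with a 90% interval for each comparison. The SAP has no sample size section, so nothing there restates or corrects the probability.

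**The concern.** A half-width quoted with a probability normally means that the observed interval will be no wider than that with the stated probability. Read so, Protocol 9.5 promises that the stated precision will be missed 1 time in 10. The stated half-widths are too narrow for that promise, given the SDs and number of participants on which they are said to rest.

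This matters because Protocol 9.1 and SAP 4.1 and 4.2 set no hypotheses and no decision rules, and there is no power statement. The precision statement is all that a reader has for judging whether 28 participants are enough.

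**Working it through.** **Inputs.** n = 28 and within-participant SD s = 0.1560 (AUCinf) and 0.2373 (Cmax), from Protocol 9.5. Two-sided 90% intervals, from Protocol 9.5 and SAP Appendix 1. The degrees of freedom (df) are not stated. A two-period crossover of A and B in 28 participants has 56 observations and 26 residual df.

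**Formula.** The standard error of B − A is s × √(2/28). The half-width not exceeded with probability q is

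h(q) = t(0.95, df) × s × √(2/28) × √(χ²(q, df)/df),

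and the probability that the observed half-width is at most w is the χ² distribution function with df degrees of freedom, evaluated at df × (w / [t × s × √(2/28)])².

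**Reproducing the plan's figures (26 df).** t(0.95, 26) = 1.7056. The standard errors are 0.1560 × √(2/28) = 0.04169 and 0.2373 × √(2/28) = 0.06342.

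| | Factor √(χ²/df) | AUCinf | Cmax |
|---|---|---|---|
| No assurance factor (plain t) | 1 | 0.0711 | 0.1082 |
| q = 0.80 | √(31.795/26) = 1.1058 | 0.07864 | 0.11962 |
| q = 0.90 | √(35.563/26) = 1.1695 | 0.0832 | 0.1265 |
| Stated in 9.5 | | 0.0786 | 0.1196 |

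The q = 0.80 row is the stated pair. Conversely, the probability of a half-width no larger than stated is 0.799 (AUCinf) and 0.800 (Cmax). Rounding of the printed inputs moves this only between 0.797 and 0.801.

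**The table in 9.5.** Each of the 14 rows has a lower limit, an upper limit and a width, so 42 entries.
- The unrounded 80% half-widths reproduce 42 of 42 to four decimals.
- The 90% half-widths on 26 df reproduce none.
- The printed, rounded 0.0786 and 0.1196 miss 9 of the 28 limits. At 80% for AUCinf, for example, 0.8 × exp(0.0786) = 0.8654, where the table has 0.8655; 0.8 × exp(0.07864) gives 0.8655.

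The table was therefore built from the unrounded 80% values.

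**The planned model.** Complete data give 14 × 3 + 14 × 2 = 70 observations. The design matrix for participant, period and treatment has rank 31, leaving 70 − 31 = 39 residual df. The variance factor for B − A remains 2/28 = 0.0714. With t(0.95, 39) = 1.6849:
- the probability of meeting the stated half-widths is 0.8654 (AUCinf) and 0.8661 (Cmax);
- the 90% half-widths are 0.0801 and 0.1218.

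A simulation of the 70-observation design with participant effects removed gave 0.866 for both. A REML simulation gave 0.863 to 0.877 (assumed between-participant SD 0.2 and 0.4, because the documents give none).

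**Is there any df at which 90% fits?** With the standard error unchanged, the stated half-widths first reach 90% at 50 df (0.9015 and 0.9021; at 49 df, 0.8988 and 0.8994). Only 39 are available from 28 participants. The nearest 90% match to the table is 49 df, which gives 0.07865 and 0.11964 and reproduces 34 of the 42 entries; it corresponds to neither the A/B crossover nor the planned model.

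**Effect on the interval at a ratio of 100%:**

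| | AUCinf | Cmax |
|---|---|---|
| As stated | 0.9244–1.0818 | 0.8873–1.1271 |
| 90% probability, 26 df | 0.9202–1.0867 | 0.8812–1.1349 |
| 90% probability, 39 df | 0.9231–1.0834 | 0.8853–1.1295 |

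**The case against.** The strongest reply is about the term. Coverage probability ordinarily means the chance that an interval contains the true value. A 90% confidence interval has 90% coverage whatever its width, so the phrase could be read as redundant rather than false, and the defect would be an undisclosed 80% assurance level. That is a fair reading of the words, and the wording needs clarifying on either reading. It does not rescue the sentence. If 90% is only the confidence level, the planned half-widths are 0.0711 and 0.1082. If ±0.0786 and ±0.1196 are treated as fixed intervals, they cover about 94% (0.0786/0.0417 = 1.885 standard errors). No reading yields the stated half-widths together with 90%.

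The 0.865 figure can also be challenged. The 13 df beyond 26 come from the fasted Period 3 data and rely on one residual variance for fed and fasted dosing. If B versus A were analysed from the A and B data alone, the figure would return to about 0.80. That stands as a limit on the 0.865, but neither basis gives 90%.

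Finally, the effect is small. An SD about 5.5% lower (0.1474 and 0.2243) would make 90% true on 26 df, and the SDs are averages over four studies whose spread is not given. This is a reason to keep the point in proportion; it does not make the stated probability correct.

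**Conclusion.** The concern holds. The half-widths and the table agree with each other and with an 80% probability; the 90% attached to them is wrong. On the 26-df basis that reproduces the figures, the risk of missing the stated precision is about 1 in 5, twice the 1 in 10 implied. Under the planned model it is about 1 in 7. Half-widths that do carry 90% are about 6% larger on 26 df and about 2% larger on 39 df.

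The 26 df are inferred, because the protocol states none; the match of all 42 entries makes the inference secure. The 39-df result assumes that all 28 participants complete, a common residual variance, and Kenward-Roger df near 39.

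All of this concerns B versus A. Treatment C is given only in Period 3 and Period 3 contains only C, so with period as a fixed effect the A versus C contrast is not estimable. That is a separate matter, and it leaves B versus A unaffected. It does mean that the figures in 9.5 should not be read as describing A versus C.

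The consequence is confined to a stated planning property. The reported intervals will come from the observed data. It should be fixed because it sits in the only quantitative justification for the sample size.

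**What to change.** Preferred: in Protocol 9.5, replace the 90% phrase with a statement that, with 80% probability, the observed half-width of the 90% interval for B versus A will not exceed the stated value (28 participants, 26 df). Every number and table row stays as it is. The cost is one sentence.

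Alternative: keep 90%, restate the half-widths as ±0.0832 and ±0.1265 on 26 df, name the B versus A comparison, and recompute the 14 rows. These values would be slightly conservative for the planned 39-df model (±0.0801 and ±0.1218).

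Neither option changes enrolment, endpoints or analysis.
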